## 344 Chapter 5: Miscellaneous Considerations

### 345 5.1 Adverse Events

346 Participants will be asked to complete questionnaires to report events that have occurred. For  
347 each event reported, the participant will be asked if the event could have been related to the use  
348 of CGM.

349 If there is no response, the participant may be contacted again to encourage questionnaire  
350 completion.

351 Participants will be asked to report the following events:

- 352 • Severe hypoglycemia
  - 353 ○ Reportable events will be defined as hypoglycemia during which the participant was  
354 impaired cognitively to the point that he/she was unable to treat himself/herself, was  
355 unable to verbalize his/her needs, was incoherent, disoriented, and/or combative, or  
356 experienced seizure or loss of consciousness.
- 357 • DKA
  - 358 ○ The participant will be asked if he/she was seen at a health care facility and/or  
359 hospitalized and what the ketone level was if known.
- 360 • Hospitalizations

361 Adverse event data reported to virtual clinic team members and study staff will be collected.

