	
 
Planned relocation to a state other than current state of residence during the study if virtual clinic is not licensed in the new state. Individuals working routinely in a state other than current state of residence in the next six months are also ineligible if the virtual clinic is not licensed in that state.
 

Sample Size	The recruitment target is 300 initiating CGM.
Outcomes	
Efficacy Outcomes: CGM use; CGM metrics for hypoglycemia (<54 and <70 mg/dL), hyperglycemia (>180 and >250 mg/dL), time in range (70-180 mg/dL), mean glucose, and glycemic variability (coefficient of variation); HbA1c; participant- reported outcomes including psychosocial and diabetes treatment satisfaction questionnaires
 
Safety Outcomes: Severe hypoglycemia, diabetic ketoacidosis, hospitalizations, and emergency room visits

Participant Duration	Study participation will be up to 12 months.

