#### 445      Safety Outcomes: Severe Hypoglycemia and DKA events, and hospitalizations

### 447      **6.4 Description of Statistical Methods**

#### 448      **6.4.1 Analysis Cohorts**

449      All subjects enrolled in the study who initiate the CGM and have a minimum amount of data as  
450      defined in the SAP will be included in the tabulations of baseline and the efficacy analyses. All  
451      subjects enrolled in this study will be included in the safety analyses.

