### 452      **6.5 Analysis of Efficacy Outcomes**

453      CGM metrics and HbA1c will be calculated and summarized at 13, 26, 39, and 52 weeks.  
454      Summary statistics for questionnaires will be provided at all time points when they are collected.

455 A linear mixed model with a random subject effect will be used to assess whether the change  
456 from baseline significantly differs from zero. If values are highly skewed, then the winsorized  
457 mean will be tested or a transformation utilized. A complete-case analysis using a paired t-test or  
458 Wilcoxon signed rank test will also be assessed.

459 **6.6 Subgroup Analyses**

460 Subgroup analyses for HbA1c and selected CGM outcomes will be performed by baseline  
461 HbA1c group, insulin delivery modality, age, healthcare provider (endocrinologist or primary  
462 care provider), and various participant characteristics as described in the SAP.

463 **6.7 Safety Analyses**

464 All adverse events that occur post enrollment will be listed in a table. Additionally, each of the  
465 following safety metrics will be tabulated for reported SH and DKA events, hospitalizations and  
466 emergency room visits:

467     • Number of subjects with  $\geq 1$  event  
468     • Number of events per subject  
469     • Incidence rate per 100 person-years

470 **6.8 Baseline Descriptive Statistics**

471 Baseline demographic and clinical characteristics of the cohort of all subjects who initiate the  
472 CGM will be summarized in a table.

473 **6.9 Multiple Comparisons/Multiplicity**

474 No adjustments for multiple comparisons will be made.

475 **6.10 Additional Analyses**

476 Several additional analyses will be performed in this study. These will include the following:

477     • Tabulations of CGM glycemia and CGM use by month and comparing the first 26 weeks  
478 and last 26 weeks of the study (overall and within subgroups)  
479     • Tabulations of CGM glycemia by time of day  
480     • Tabulations of the number of participant contacts with the virtual clinic  
481     • Bivariate relationship between questionnaires and glycemic metrics following CGM  
482 initiation

483 **Chapter 7: Ethics/Protection of Human Participants**

484 **7.1 Ethical Standard**

485 The investigator will ensure that this study is conducted in full conformity with Regulations for  
486 the Protection of Human Participants of Research codified in 45 CFR Part 46, 21 CFR Part 50,  
487 21 CFR Part 56, and/or the ICH E6.

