7.4 Statistical Methods

For all outcomes, summary statistics appropriate to the distribution will be tabulated on a subject level overall and within the subgroups defined in Section 12. For the CGM metrics, summary statistics appropriate to the distribution also will be tabulated for each 4-week interval and for the first and last 26 weeks of the study. For the questionnaires, summary statistics will be reported for the mean scores in addition to the individual responses for each question.

For all outcomes, a linear mixed model with a random subject effect will be used to test whether the mean change from baseline significantly differs from zero. These models will be fit for each of the subject level CGM metrics and HbA1c at 13, 26, 39, and 52 weeks. They also will be fit for the questionnaires at 26 and 52 weeks. If values are skewed, then winsorization will be utilized. Point estimates and 95% confidence intervals for change in glycemic outcomes will be reported.

For the three mental health screening questionnaires, only summary statistics will be tabulated. The three mental health screening questionnaires falling under this umbrella are the Patient

187 Health Questionnaire-8, the Diabetes Distress Scale (Management Distress Subscale), and the
188 Fear of Hypoglycemia Survey (Worry Subscale).

189 **7.5 Analyses Windows**

190 For HbA1c, only measurements occurring within ± 45 days of the target measurement date at a
191 given time point will be included in the tabulation of summary statistics. The windows for
192 glycemic metrics were defined above in Section 7.1.

193 **7.6 Sensitivity Analyses**

194 For CGM and HbA1c outcomes, a complete-case analysis restricting to non-missing outcomes
195 will also be assessed. A paired t-test (for normally distributed outcomes) or a Wilcoxon signed
196 rank test (for skewed outcomes) will be used.

197 **8 Safety Analyses**

198 All adverse events that occur on or after the date of enrollment will be listed in a table.

199 For events occurring on or after the date of CGM initiation, the reported safety outcomes include
200 diabetic ketoacidosis (DKA), severe hypoglycemia (SH), hospitalization, and emergency room
201 visits. The following statistics will be tabulated for each safety outcome:

- 202 • Total number of events
- 203 • Number and proportion of subjects with an event (discretized into bins)
- 204 • Incidence rate per 100 person years

205

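### Emergency room visits have a planned safety incidence rate, but no solicited or defined collection route, so the rate is liable to be too low

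*Protocol*

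**What the plan says.** ER visits appear as a safety outcome in three places.

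- The Outcomes row of the Protocol Summary gives the safety outcomes as "Severe hypoglycemia, diabetic ketoacidosis, hospitalizations, and emergency room visits". The SAP overview table repeats this.
- Protocol 6.7 says that the "following safety metrics will be tabulated for reported SH and DKA events, hospitalizations and" (the sentence runs on to ER visits). One of those metrics is "Incidence rate per 100 person-years".
- SAP 8 names "diabetic ketoacidosis (DKA), severe hypoglycemia (SH), hospitalization, and emergency room" visits as the reported safety outcomes and plans for each an "Incidence rate per 100 person years". It defines person-years as running from CGM initiation to the last day of follow-up.

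Two other places leave them out.

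- Protocol 5.1 introduces its list with "Participants will be asked to report the following events". The list has three entries: severe hypoglycemia, DKA and hospitalizations.
- The safety line of Protocol 6.3 covers "Severe Hypoglycemia and DKA events, and hospitalizations" only.

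Protocol 6.3 also has healthcare utilization among its efficacy outcomes, and SAP 5 gives ER visits as one example of service utilization. Neither says where those data come from.

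**The concern.** A rate needs its numerator events to be sought over the same time that the denominator counts. Here the denominator is all follow-up from CGM initiation, but the only list of events put to participants does not include ER visits. The study is remote and its questionnaires are self-reported, so the documents describe no site record that would pick up what a participant is not asked about. A visit that goes unrecorded takes an event from the numerator and no time from the denominator.

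At stake is the reading of one safety rate. A low ER rate could be taken as reassurance about remote CGM initiation when it partly reflects that nobody asked. The problem could grow over time, because scheduled virtual clinic contact gives way to as-needed contact after 26 weeks while person-time continues to accrue.

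**Working it through.** **Step 1: compare the safety lists.**

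| Place | Severe hypoglycemia | DKA | Hospitalization | ER visit |
|---|---|---|---|---|
| Protocol Summary, Outcomes | yes | yes | yes | yes |
| Protocol 6.7 (tabulated, with rate) | yes | yes | yes | yes |
| SAP 8 (tabulated, with rate) | yes | yes | yes | yes |
| Protocol 6.3, safety line | yes | yes | yes | **no** |
| Protocol 5.1, asked of participants | yes | yes | yes | **no** |

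The protocol disagrees with itself whatever the data source turns out to be.

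**Step 2: look for another collection route.**

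- *DKA item in 5.1.* It asks whether the participant was seen at a health care facility. It covers DKA only and is not specific to an ER. The severe hypoglycemia item, as written, has no such question.
- *Unsolicited reports.* 5.1 also collects adverse event data that reach the virtual clinic team or study staff. This is a real route, but it depends on what the participant mentions.
- *Utilization outcomes.* Protocol 6.3 and SAP 5 name outcomes, not sources. Neither the follow-up data list in Protocol 3.6 nor the questionnaire table in Chapter 4 shows a utilization instrument or claims feed. Insurers appear as a recruitment channel and for CGM coverage, not as a data source. SAP 8 does not say that utilization data feed the safety rate.

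The events left exposed are mainly ER visits without admission that are not part of a reported severe hypoglycemia or DKA event.

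**Step 3: direction of any bias.** Let *r* be the true rate and *c* the fraction of visits captured. Since the denominator is all person-time,

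observed rate = *c* × *r*, and relative shortfall = 1 − *c*.

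With *c* between 0 and 1 the bias is downward or nil.

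**Step 4: scale, by illustration only.** The plan has no figure to reproduce: it states no ER rate, expected count or capture fraction, and Protocol 6.2 calls the sample a convenience sample. The inputs below are assumptions, apart from the 300 participants and the follow-up lengths.

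- Person-years: 300 participants × 0.5 year = 150, or × 1 year = 300. The upper figure needs all 300 to complete the optional second 26 weeks.
- True rate *r*: 20 per 100 person-years (assumed; 10 and 40 were also tried).
- Capture *c*: 40% to 100% (assumed).

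Events counted = *r* × person-years / 100 × *c*. Limits are exact Poisson 95%.

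| Capture | Observed rate per 100 | 300 person-years: events (95% limits) | 150 person-years: events (95% limits) |
|---|---|---|---|
| 100% | 20.0 | 60 (15.3–25.7) | 30 (13.5–28.6) |
| 80% | 16.0 | 48 (11.8–21.2) | 24 (10.3–23.8) |
| 60% | 12.0 | 36 (8.4–16.6) | 18 (7.1–19.0) |
| 40% | 8.0 | 24 (5.1–11.9) | 12 (4.1–14.0) |

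At 60% and 40% capture the interval excludes the assumed true rate of 20 for both amounts of follow-up. With *r* = 10 the observed rate runs from 4.0 to 10.0, and with *r* = 40 from 16.0 to 40.0, over the same capture range. The table shows only that incomplete capture could outweigh sampling error. It does not estimate what will happen in this study.

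**The case against.** The strongest reply is that a gap in 5.1 is not proof of a gap in the data. The event form itself is not in the documents, and Chapter 4 leaves questionnaire administration to a procedures manual, so the form may already ask about ER visits. SAP 5 lists ER visits beside cost of care and filled prescriptions. Neither of those is in 5.1 either, which hints at a separate utilization source, although the documents do not say so. Scheduled team contact through the first 26 weeks gives participants occasions to mention a visit.

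This stands against a stronger reading that a reader might draw: that the ER rate will be undercounted, or that it will be low by some stated percentage or number of visits. The documents do not support either. Complete capture cannot be ruled out, and any percentage shortfall simply restates an assumed capture fraction. It does not remove the conflict between the lists, or the fact that no route to the SAP 8 numerator is defined.

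The study is also single-arm, with no primary outcome, no formal stopping guidelines and only exploratory analyses. No decision rule depends on the ER rate, and the other three safety outcomes are all solicited. That limits how much weight the point should carry, but not the case for a cheap correction.

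**Conclusion.** The inconsistency is certain: ER visits have a planned safety rate, are missing from the solicited events in Protocol 5.1 and from the safety line in Protocol 6.3, and have no named source elsewhere. The consequence is a risk rather than a demonstrated bias. If the plan is followed as written, some visits are liable to be missed, and any resulting error lowers the rate. This rests on two assumptions: that 5.1 reflects what the event questionnaire asks, and that no complete utilization source feeds SAP 8. If either fails, the shortfall may be small or zero. The documents allow no estimate of its size. The point is worth correcting, but it does not threaten the study's main results.

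**What to change.** First, make the safety outcome lists in the Protocol Summary, Protocol 5.1, 6.3 and 6.7, and SAP 8 agree. Then do one of the following.

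1. Add ER visits, with date and reason, to the 5.1 list and the existing event questionnaire. Ask participants already enrolled about the whole period since their CGM initiation. Without that look-back, visits before the change would be ascertained less completely than visits after it.
2. If a utilization source already captures ER visits, name it in the protocol and SAP, give the period and participants it covers, and state that it supplies the numerator of the SAP 8 rate.

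The first option costs one questionnaire item and an amendment, which Protocol 7.2 requires the IRB to approve before it is implemented. It also brings some recall error for visits before the change. The second needs only added text, provided the source exists and its coverage matches the person-time in the denominator.

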### 362 5.2 Device Issues

363 Participants will also be asked to report the following device issues:

- 364 • Device-related events with potential impact on participant safety
  - 365 ○ Skin reactions at the sensor site will be reported as adverse events if they are  
366 classified as severe and/or required treatment.

### 367 5.3 Study Costs

368 CGM supplies will be provided for the first six months of the study. Participants will be able to  
369 keep the provided CGM supplies after follow up has ended. Participants who plan to continue  
370 use of CGM after 6 months will need to work with their insurance provider to obtain approval  
371 for CGM.

372 Costs of standard medical care for diabetes that would occur even if the participant were not in  
373 this study, including insulin, will be the participant's responsibility.

### 374 5.4 Participant Compensation

375 Participant compensation will be specified in the informed consent form.

### 376 5.5 Participant Withdrawal

377 Participation in the study is voluntary, and a participant may withdraw at any time. The reason  
378 for withdrawal will be collected. Additionally, at the time of withdrawal, the participant will be

379 asked to complete device downloads and questionnaires. For participants who withdraw, their  
380 data will be used up until the time of withdrawal.

381 Participants who do not complete baseline procedures in a timely fashion or are noncompliant  
382 with respect to the protocol may be withdrawn.

383 **5.5.1 Pregnancy**

384 If pregnancy occurs, the participant will be withdrawn from the study.

385 **5.6 Contact Information**

386 Contact information for each participant, including name, email address, mobile number, and  
387 mailing address will be provided to the coordinating center, the Jaeb Center for Health Research  
388 in Tampa, FL. Permission to obtain such information will be included in the Informed Consent  
389 Form. The contact information for the study will be maintained in a secure database and will be  
390 maintained separately from study data.

391 Contact information is necessary for shipment of study supplies, set up of certain apps needed for  
392 the study on the participant's personal smartphone, and participant payments. Contact  
393 information will be used by virtual clinic team members for training and follow up. Participants  
394 will receive reminders via text, email, or phone to complete questionnaires or submit study data.  
395 Mobile number will be shared with parties involved in processing of data if the mobile number is  
396 required to send automated text reminders to minimize missing data.

397 Communications will be provided to a health care provider designated by the participant.

398 **5.6.1 Personal Healthcare Provider Information**

399 Participants will be asked to provide the contact information of a health care provider that they  
400 designate for their diabetes management. Provider information is necessary so that the provider  
401 can be made aware of the participant's study participation and of information related to care or  
402 treatment. Permission for communication to the designated health care provider will be included  
403 in the Informed Consent Form.

404 **5.7 Confidentiality**

405 For security purposes, participants will be assigned an identifier that will be used instead of their  
406 name. Protected health information gathered for this study will be shared with the JCHR  
407 coordinating center in Tampa, FL, virtual clinic and study team members involved with  
408 participant training and review of CGM data, participating institutions and investigators in the  
409 research study, and parties involved in collecting and processing of data in accordance with the  
410 terms of the study contracts. Participant calls with the virtual team members may be recorded.  
411 The informed consent form will specify entities that will have access to or receive data.

412 No identifiable health information of an enrolled participant will be released by the coordinating  
413 center, except as described above.

414 **5.8 Quality Assurance and Monitoring**

415 Designated personnel from the coordinating center will be responsible for maintaining quality  
416 assurance and quality control systems to ensure that the trial is conducted, and that data are

417 generated, documented and reported in compliance with the protocol, GCP and the applicable  
418 regulatory requirements.

## 419      **Chapter 6: Statistical Considerations**

### 420      **6.1 Statistical and Analysis Plan**

421      The approach to sample size and statistical analyses are summarized below. A Statistical  
422      Analysis Plan (SAP) will be written and finalized prior to the completion of the study. The  
423      analysis plan synopsis in this chapter contains the framework of the anticipated final SAP. The  
424      SAP will describe the analyses to be performed for the primary manuscript.

### 425      **6.2 Sample Size**

426      The goal for the study is to include at least 300 participants who initiate training for CGM. This  
427      is a convenience sample and not based on statistical principles.

### 428      **6.3 Outcome Measures**

429      The following outcome measures will be stratified by type of diabetes.

#### 430      Efficacy Outcomes:

- 431      • HbA1c
- 432      • CGM use
- 433      • Mean of sensor glucose levels
- 434      • Percentage of time spent with sensor glucose levels <54 and <70 mg/dL
- 435      • Percentage of time spent with sensor glucose levels >180 and >250 mg/dL
- 436      • Percentage of time spent with sensor glucose levels in the target range (70-180 mg/dL)
- 437      • Glycemic variability measured by the coefficient of variation
- 438      • Insulin metrics
- 439      • Questionnaire scores (and their corresponding subscales)
- 440      • Psychosocial metrics
- 441      • Healthcare utilization metrics

442      CGM, HbA1c, and questionnaires outcomes will be evaluated at all time points they are  
443      collected.

#### 445      Safety Outcomes: Severe Hypoglycemia and DKA events, and hospitalizations

### 447      **6.4 Description of Statistical Methods**

#### 448      **6.4.1 Analysis Cohorts**

449      All subjects enrolled in the study who initiate the CGM and have a minimum amount of data as  
450      defined in the SAP will be included in the tabulations of baseline and the efficacy analyses. All  
451      subjects enrolled in this study will be included in the safety analyses.

### 452      **6.5 Analysis of Efficacy Outcomes**

453      CGM metrics and HbA1c will be calculated and summarized at 13, 26, 39, and 52 weeks.  
454      Summary statistics for questionnaires will be provided at all time points when they are collected.

455 A linear mixed model with a random subject effect will be used to assess whether the change  
456 from baseline significantly differs from zero. If values are highly skewed, then the winsorized  
457 mean will be tested or a transformation utilized. A complete-case analysis using a paired t-test or  
458 Wilcoxon signed rank test will also be assessed.

459 **6.6 Subgroup Analyses**

460 Subgroup analyses for HbA1c and selected CGM outcomes will be performed by baseline  
461 HbA1c group, insulin delivery modality, age, healthcare provider (endocrinologist or primary  
462 care provider), and various participant characteristics as described in the SAP.

463 **6.7 Safety Analyses**

464 All adverse events that occur post enrollment will be listed in a table. Additionally, each of the  
465 following safety metrics will be tabulated for reported SH and DKA events, hospitalizations and  
466 emergency room visits:

467     • Number of subjects with  $\geq 1$  event  
468     • Number of events per subject  
469     • Incidence rate per 100 person-years

470 **6.8 Baseline Descriptive Statistics**

471 Baseline demographic and clinical characteristics of the cohort of all subjects who initiate the  
472 CGM will be summarized in a table.

473 **6.9 Multiple Comparisons/Multiplicity**

474 No adjustments for multiple comparisons will be made.

475 **6.10 Additional Analyses**

476 Several additional analyses will be performed in this study. These will include the following:

477     • Tabulations of CGM glycemia and CGM use by month and comparing the first 26 weeks  
478 and last 26 weeks of the study (overall and within subgroups)  
479     • Tabulations of CGM glycemia by time of day  
480     • Tabulations of the number of participant contacts with the virtual clinic  
481     • Bivariate relationship between questionnaires and glycemic metrics following CGM  
482 initiation

483 **Chapter 7: Ethics/Protection of Human Participants**

484 **7.1 Ethical Standard**

485 The investigator will ensure that this study is conducted in full conformity with Regulations for  
486 the Protection of Human Participants of Research codified in 45 CFR Part 46, 21 CFR Part 50,  
487 21 CFR Part 56, and/or the ICH E6.

488 **7.2 Institutional Review Boards**

489 The protocol, informed consent form(s), recruitment materials, and all participant materials will  
490 be submitted to the IRB for review and approval. Approval of both the protocol and the consent  
491 form must be obtained before any participant is enrolled. Any amendment to the protocol will  
492 require review and approval by the IRB before the changes are implemented to the study. All  
493 changes to the consent form will be IRB approved; a determination will be made regarding  
494 whether previously consented participants need to be re-consented.

495 **7.3 Informed Consent Process**

496 **7.3.1 Consent Procedures and Documentation**

497 Informed consent is a process that is initiated prior to the individual's agreeing to participate in  
498 the study and continues throughout the individual's study participation. Individuals who indicate  
499 that they are interested in study participation will be directed to a website with information about  
500 the study. Interested individuals will be able to have a live chat or arrange for a phone call to  
501 answer questions about the study as part of the informed consent process. Participants who want  
502 to participate in the study will sign the IRB-approved electronic consent form.

503 The participants should have the opportunity to discuss the study with their surrogates or think  
504 about it prior to agreeing to participate. The participant will sign the informed consent document  
505 prior to any procedures being done specifically for the study. The participant may withdraw  
506 consent at any time throughout the course of the study. The participant will be able to print a  
507 copy of the informed consent document for their records. The rights and welfare of the  
508 participants will be protected by emphasizing to them that the quality of their medical care will  
509 not be adversely affected if they decline to participate in this study.

510

